#### 4.2. Variable Definitions

#### 4.2.1. Body Mass Index

Body mass index will be calculated as follows:

BMI  $(kg/m^2) = [weight (kg)] / [height (m)]^2$ 

#### 4.2.2. Prior and Concomitant Medication

Prior medication is defined as any nonstudy medication started and stopped before the first dose of itacitinib.

Concomitant medication is defined as any nonstudy medication that is started accordingly:

- Before the date of first administration of itacitinib and is ongoing throughout the study or ends on/after the date of first administration of itacitinib.
- On/after the date of first administration of itacitinib and is ongoing or ends during the course of the study.

A prior medication could also be classified as "both prior and concomitant medication" if the end date is on or after first dose of itacitinib. In the listing, it will be indicated whether a medication is prior-only, concomitant-only, or both prior and concomitant.

For the purposes of analysis, all medications will be considered concomitant medications unless the medications can unequivocally be defined as not concomitant.

#### 4.2.3. Creatinine Clearance

Creatinine clearance by Cockcroft-Gault equation (Cockcroft and Gault 1976) is estimated from serum creatinine (mg/dL) determination using the following formula:

Creatinine clearance (mL/min) =  $[140 - age (years)] \times weight (kg) \times \{0.85 \text{ for female participants}\} / [72 \times serum creatinine (mg/dL)]$ 

#### 5. STATISTICAL METHODOLOGY

### **5.1.** General Methodology

Unless otherwise noted, SAS® software (SAS Institute Inc, Cary, NC; v9.4 or later) will be used for the generation of all tables, graphs, and statistical analyses. Descriptive summaries for continuous variables will include, but not be limited to, the number of observations, mean, standard deviation, median, minimum, and maximum. Descriptive summaries for categorical variables will include the number and percentage of participants in each category.

### **5.2.** Treatment Groups

In Phase 1, a total of 24 participants with Grade 1, 2, or 3 BOS will be assigned to receive 1 of 3 itacitinib dose levels (n = 8 each).

In Phase 2, participants will be treated with itacitinib at the RP2D.

### 5.3. Analysis Populations

#### 5.3.1. Full Analysis Set

The FAS will include all participants enrolled in the study who received at least 1 dose of itacitinib. The FAS will be used for the summary of demographics, baseline characteristics, participant disposition, and analyses of all safety, study treatment administration, and efficacy data.

### **5.3.2.** Pharmacokinetic-Evaluable Population

The PK-evaluable population consists of all enrolled participants who received at least 1 dose of itacitinib and provided at least 1 postdose PK sample.

### 6. BASELINE, EXPOSURE, AND DISPOSITION

Appendix A provides a list of data displays. Sample data displays are included in a separate document.

### 6.1. Demographics, Baseline Characteristics, and Medical History

Demographics, baseline characteristics, medical history, lung transplant history, BOS history, prior and concomitant medications for immunosuppression, and prior and concomitant medications for treatment of BOS will be summarized for the FAS and listed. Procedures and nondrug therapies will be listed for the FAS.

### 6.1.1. Demographics and Baseline Characteristics

Demographics and baseline characteristics include the following: age, sex, race, ethnicity, weight, height, and BMI.

### **6.1.2. Medical History**

For participants in the FAS, medical history will be summarized. This summation will include the number and percentage of participants with significant medical history for each body system/organ class as documented on the eCRF.

#### 6.1.3. Lung Transplant History

Time since double lung transplant, indication for transplant, donor CMV status, recipient CMV status, donor EBV status, recipient EBV status, history of acute rejection, history of primary graft dysfunction, history of donor-specific antibodies, history of gastroesophageal reflux disease, history of CMV pneumonitis, history of colonization with aspergillus, post-transplant baseline FEV1 (absolute and % predicted), and best post-transplant forced vital capacity will be summarized descriptively. Among these variables, summaries for continuous variables will include but not be limited to the number of observations, mean, standard deviation, median, minimum, and maximum. Summaries for categorical variables will include the number and percentage of participants in each category.

#### 6.1.4. Bronchiolitis Obliterans Syndrome History

Time since BOS diagnosis, BOS grade at diagnosis, BOS grade at screening, augmented immunosuppression since onset of BOS (other than ECP), and ECP will be summarized.

### **6.1.5.** Medications for Immunosuppression

Medications for immunosuppression will be coded using the WHO Drug Dictionary. For participants in the FAS, the number and percentage of participants with medications for immunosuppression will be summarized separately for the 3 categories of induction, maintenance, and treatment for acute rejection. Within each category, the summary will be by WHO drug class and WHO drug term.

#### 6.1.6. Medications for Treatment of Bronchiolitis Obliterans Syndrome

Prior medications for treatment of BOS will be coded using the WHO Drug Dictionary. For participants in the FAS, the number and percentage of participants with prior medications for treatment of BOS will be summarized by WHO drug class and WHO drug term.

### **6.2.** Disposition of Participants

The number and percentage of participants who were randomized, who were treated, who discontinued study treatment with a primary reason for discontinuation, and who withdrew from the study with a primary reason for withdrawal will be summarized for the FAS. The number of participants enrolled by country and/or site will also be provided by treatment group.

#### **6.3.** Protocol Deviations

Protocol deviations recorded on the eCRF will be summarized and listed.

### 6.4. Exposure

For participants in the FAS, exposure to itacitinib will be summarized descriptively as follows:

#### • Duration of treatment with itacitinib:

Duration of treatment (days) = date of last dose of itacitinib – date of first dose of itacitinib + 1

### • Average daily dose of itacitinib:

Average daily dose of itacitinib (mg/day) = [total actual dose taken (mg)] / [duration of treatment with itacitinib (days) – days of itacitinib interruption]

#### • Dose modifications of itacitinib:

Number of participants who had itacitinib dose reduction and/or interruption

# 6.5. Study Drug Compliance

For participants in the FAS, overall compliance (%) for itacitinib will be calculated for all participants as follows:

Overall compliance (%) =  $100 \times [\text{total dose actually taken (mg)}] / [\text{total prescribed dose (mg)}]$ 

The total prescribed dose is defined as the sum of the doses prescribed by the investigator accounting for dose modifications.

#### 6.6. Prior and Concomitant Medication

Prior medications and concomitant medications (excluding medications for immunosuppression and treatment for BOS) will be coded using the WHO Drug Dictionary. For participants in the FAS, the number and percentage of participants each with prior and concomitant medications will be summarized by WHO drug class and WHO drug term. In the data listing, each medication will be recorded as prior, concomitant, or both prior and concomitant.

#### 7. EFFICACY

Appendix A provides a list of data displays. Sample data displays are included in a separate document.

### 7.1. General Considerations

All efficacy analyses will be done by treatment group using the FAS. The SGRQ Total Score, QOL-SF-12 Questionnaire, and EQ-5D-3L analyses will not be performed due to the early study termination.

For continuous measurements, summary statistics will include sample size, mean, median, standard deviation, standard error of the mean, minimum, and maximum. For all continuous variables, both the actual value and change and/or percentage from baseline (if available) will be analyzed. For categorical measurements, summary statistics will include sample size, frequency, and percentages.

All by-visit analyses will include the EOT and follow-up visits if the data are available.

### 7.2. Efficacy Hypotheses

Not applicable.

### 7.3. Analysis of the Primary Efficacy Parameter

In Phase 1, the primary endpoint is FEV1. Change and percentage change from baseline in FEV1 and FEV1 % predicted will be summarized by visit and treatment group.

In Phase 2, the primary endpoint is  $FEV_1$  response rate through the Week 12 visit, defined as the proportion of participants demonstrating a  $\geq 10\%$  absolute increase in  $FEV_1$  compared with baseline, confirmed by 2 consecutive spirometric assessments  $\geq 1$  week apart. The primary analysis will be conducted once the last participant completes the Week 12 visit or withdraws from the study. If a participant withdraws from the study before Week 12, or there is no  $FEV_1$  data up to and including Week 12, the participant will be considered as a nonresponder. Summary statistics and 95% CIs will be provided. Confidence intervals will be calculated based on the exact method for binomial distributions.

In Phase 1,  $FEV_1$  response rate will also be calculated due to the fact that duration of  $FEV_1$  response is a secondary efficacy endpoint in Phase 1.

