7. DISCONTINUATION OF STUDY TREATMENT AND PARTICIPANT DISCONTINUATION/WITHDRAWAL

7.1. Discontinuation of Study Treatment

7.1.1. Reasons for Discontinuation

Participants **must** be discontinued from study treatment for the following reasons:

- BOS progression, defined as a $\geq 10\%$ absolute decrease in FEV₁ from pretreatment baseline, observed in at least 2 consecutive spirometric assessments at least 3 weeks apart.

Note: If the investigator believes that the participant has met criteria for BOS progression due to another reason (eg, infection), then continuation of treatment may be permitted after discussion with the medical monitor.

- An unacceptable toxicity is observed. An unacceptable toxicity is defined as an AE that is related to study treatment that, in the judgment of the investigator or the sponsor's medical monitor, compromises the participant's ability to continue study-specific procedures or is considered to not be in the participant's best interest.
- The investigator determines that there has been a loss of clinical benefit in the absence of Protocol-defined BOS progression.
- Development of post-transplant lymphoproliferative disorder.
- Development of BK viremia.

- Consent is withdrawn.
Note: Consent withdrawn means that the participant has explicitly indicated that they do not want to be followed any longer; in this case, no further data, except data in public domain, may be solicited from or collected on the participant. Participants may choose to discontinue study treatment and remain in the study to be followed for progression and survival.
- Further participation would be injurious to the participant's health or well-being, in the investigator's medical judgment.
- The study is terminated by the sponsor.
- The study is terminated by the local health authority, IRB, or IEC.

A participant **may** be discontinued from study treatment as follows:

- If, during the course of the study, a participant is found not to have met eligibility criteria, the medical monitor, in collaboration with the investigator, will determine whether the participant should be withdrawn from study treatment.
- If a participant is noncompliant with study procedures or study drug/treatment administration in the investigator's opinion, the sponsor should be consulted for instruction on handling the participant.

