8.5. End of Treatment and/or Early Termination

When the participant permanently discontinues study drug, the EOT visit should be conducted. If the EOT visit coincides with a regular study visit, the EOT evaluations will supersede those of that scheduled visit, and the data should be entered in the EOT visit in the eCRF. The participant should be encouraged to return for the follow-up visit.

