#### 4.1.4. Last Available Value

The last available value is the last nonmissing measurement obtained after starting itacitinib.

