#### 4.1.5. Handling of Missing and Incomplete Data

In general, values for missing data will not be imputed unless methods for handling missing data are specified in this section or relevant sections.

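### Phase 1 nominal-visit FEV1 means leave out participants who stopped for progression, so they sit above the treated cohort's mean: usually slightly at Week 12, more at later visits

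*SAP*

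**What the plan says.** SAP 7.3 states "In Phase 1, the primary endpoint is FEV 1". The objectives tables (Protocol Table 6, SAP Table 1) are broader: they list FEV1 change beside adverse events, laboratory parameters, PK and PD. The planned continuous analysis is change and percentage change in FEV1 and in FEV1 % "predicted will be summarized by visit and treatment group", produced as SAP Table 2.2.1.

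Four other provisions decide who is in each row:

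- **Stopping.** Protocol 7.1.1 says participants must "be discontinued from study treatment for the following reasons". The first reason is a fall of at least 10% from pretreatment baseline, "observed in at least 2 consecutive spirometric assessments at least 3 weeks apart". If the investigator attributes the fall to another cause, "then continuation of treatment may be permitted after discussion with the medical monitor".
- **Recording.** Under Protocol 8.5, when the EOT visit falls on a regular visit, "the EOT evaluations will supersede those of that scheduled visit, and the data should be entered in the EOT visit in the eCRF".
- **Schedule.** Protocol Table 2, as far as its broken text can be read, marks spirometry from screening to EOT and not at safety follow-up.
- **Missing data.** SAP 4.1.5 says "values for missing data will not be imputed unless methods for handling missing data are specified". The only missing-data rule in SAP 7.3 is the nonresponder rule, which concerns response rate and not the continuous summary.

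SAP 7.1 includes EOT and any follow-up visits in by-visit analyses. No SAP rule returns an EOT value to its calendar week. SAP 4.1.4 says "The last available value is the last nonmissing measurement obtained after starting itacitinib", but no efficacy section or Appendix A output is said to use it for FEV1.

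**The concern.** The variable being summarised also decides who remains to be summarised. A participant whose FEV1 falls and stays down leaves every later row. If the stopping visit coincides with a scheduled one, the confirming low value leaves its own week too; only the first low value stays where it was measured. Each later row then describes the participants who have done better so far.

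What is at stake is how the Phase 1 FEV1 results by dose level are read. A dose level with more early progressors loses more low values and so gains more from the exclusion. With 8 participants per dose level, one or two stoppers can change the sign of a mean.

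**Working it through.** The plan states no figure for this quantity, so there is none to reproduce.

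**When the effect starts.** On-treatment spirometry is at Weeks 1, 2, 4, 8 and 12, then every 4 weeks. Two readings at least 3 weeks apart are first available at Week 4 (if Weeks 1, 2 and 4 are all low) or Week 8 (if Weeks 4 and 8 are). So the rows can be affected from Week 4 to 8 onward.

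**Arithmetic at n = 8 (invented values).** Changes of +8, +4, +2, 0, -2, -4, -14 and -18 have mean (14 - 38)/8 = -3.0. If the two largest decliners have stopped, the row shows (14 - 6)/6 = +1.3.

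**Base-case simulation (assumptions, not document figures).** Individual FEV1 slopes are linear, with mean -3% and SD 5% per 12 weeks. Visit-to-visit CV is 5%, with a single noisy baseline. The 10% fall is read as relative to baseline. Every confirmed faller stops, and every stopping value goes to EOT.

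| Week | Mean if all were followed | Nominal-visit row | Bias (points) | Still in row |
|---|---|---|---|---|
| 12 | -2.7% | -1.6% | 1.1 | 91% |
| 24 | -5.8% | -0.5% | 5.3 | 70% |
| 36 | -8.8% | +2.4% | 11.2 | 55% |

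With a true mean change of about zero, the Week 24 row shows +3.3%. I re-ran this case and it agreed to within 0.1 point.

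**Milder assumptions.**

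- Slope SD 3 instead of 5: the table shows -2.0, -2.8 and -2.0% at Weeks 12, 24 and 36, which is flat.
- Slope SD 2 and CV 3%: it shows -2.8, -4.8 and -5.1%, which still falls.
- Stopping only at a 20% relative fall (one possible meaning of a 10-point absolute fall in % predicted, for someone at 50% predicted): Week 12 bias is about 0 and Week 24 bias is 1.3 points, with 94% remaining.

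**Wider grid.** Nine scenarios crossed mean slopes of 0, -5 and -10% per 12 weeks with slope SDs of 5, 10 and 15, at within-participant SD 5.

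- The bias was upward in all nine: +0.2 to +8.1 points at Week 12 and +2.2 to +28.5 at Week 24.
- In the middle scenario (slope -5, SD 10) the cohort means at Weeks 12 and 24 are -5.0 and -10.1. The rows show -2.3 and +4.0, and the EOT row averages -18.4.
- If 20% are exempt from stopping in that scenario, the bias is still +2.1 and +9.7 points.

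**What each repair recovers (base case).**

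| Week | Cohort | Row as planned | EOT value returned to its week | Last on-treatment value, all participants |
|---|---|---|---|---|
| 12 | -2.7% | -1.6% | -2.3% | -2.8% |
| 24 | -5.8% | -0.5% | -2.0% | -5.1% |

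Returning EOT values to their week closes 0.7 of the 1.1-point gap at Week 12, but only 1.5 of the 5.3 points at Week 24. The rest of the later gap exists because there is no FEV1 after stopping.

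**The case against.** The strongest reply is that little depends on these rows and that the decliners are reported elsewhere. Much of it stands.

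- **Dose selection.** A reader might infer that the table could steer the choice of the recommended Phase 2 dose. The documents do not support that. Protocol 4.1 and 6.1.1 base the choice on adverse events, laboratory data, PK and PD through Week 12, with an FEV1 response analysis. Protocol 2.3 records the decision not to proceed to Phase 2 after a September 2021 analysis, and SAP section 11 dates the SAP to April 2023 and August 2024.
- **Lost data.** A reader might also infer that decliners vanish from the report. They do not. SAP 7.1 shows an EOT row, SAP 7.4.2 counts progression and death as events by treatment group, SAP 6.2 gives reasons for stopping, and the FEV1 data are listed. But the EOT row pools people who stopped at different times, and none of these outputs corrects the Week 12, 16 or 24 means.
- **Conditions.** Stopping has an exception. The move to EOT applies only when the visits coincide; a separate EOT visit leaves the confirming value in place, though later rows still lose the participant.
- **Descriptive status.** No hypothesis is tested and no formal comparison between doses is planned. That limits the consequence, but it does not make the row means describe the treated cohort.
- **Schedule version.** SAP 3.4 refers to the Amendment 3 schedule, while the protocol in hand is Amendment 5. I could check post-EOT spirometry only in the latter.

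**Conclusion.** The point holds as a bias in the nominal-visit rows. Their means are pushed upward relative to all treated participants, and that direction held in every scenario examined. At Week 12 the bias is about 0 to 1.3 points under moderate assumptions and up to about 8 under steeper or more variable slopes; it is larger at later visits.

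A reader might go further and expect the table to show FEV1 rising while the cohort declines. That happens in some scenarios and not in others. It depends on slopes and SDs that the documents do not give, and on whether the 10% absolute change means relative FEV1 or points of % predicted. The linear model also lets decliners keep falling after they stop, which makes the late bias larger than it would be under a plateau.

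The consequence is limited to interpreting the Phase 1 FEV1 results by dose level. SAP Amendment 1, written for early termination, kept Table 2.2.1, so the summary is still planned and a cheap correction is worth making.

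**What to change.** In SAP 7.3 and Table 2.2.1:

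1. Assign each EOT FEV1 to the scheduled visit whose window contains its study day, and keep the EOT row. Three rules are needed. If the visit already has a scheduled value, keep that value. The 7-day windows leave gaps (28 - 7 - 7 = 14 days between 4-weekly visits), and an EOT value in a gap stays in the EOT row only. The 14-day windows from Week 16 meet at the midpoint (28 - 14 - 14 = 0), so a tie rule is needed.
2. Add, by dose level on the full analysis set, a supportive change from baseline to the last on-treatment FEV1 (including EOT) up to Week 12 and up to Week 24. State that this narrows the SAP 4.1.4 definition, which has no on-treatment or week limit. State also that it is a last-observation summary: it freezes each stopper at the stopping value and mixes times.
3. Footnote each later visit with the number at that dose level who had stopped for progression by then.

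A repeated-measures mixed model is optional; with 8 per dose level it would be fragile.

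The cost is SAP wording and a little more programming. No new data are needed and clinical management does not change. The later-visit FEV1 means will probably look less favourable.

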10.4. Statistical Analyses

10.4.1. Primary Analysis

The primary endpoint is FEV₁ response rate through the Week 12 visit, defined as the proportion of participants demonstrating a $\geq 10\%$ absolute increase in FEV₁ compared to baseline. The primary analysis will be conducted once the last participant completes the Week 12 visit or withdraws from the study. If a participant withdraws from the study before Week 12, or there is no FEV₁ data up to and including Week 12, then the participant will be considered a nonresponder.

Summary statistics and 95% CI will be provided.

Primary efficacy analysis will be conducted for the full analysis data set.

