# 7.4. Analysis of the Secondary Efficacy Parameter

#### 7.4.1. Duration of FEV1 Response

Duration of FEV1 response is defined as the interval between the onset of response and the earliest of BOS progression, loss of clinical benefit as determined by the investigator, or death, in which:

• The time of onset of response is defined as the earliest assessment date when ≥ 10% absolute increase in FEV1 compared with pretreatment baseline (confirmed by 2 consecutive spirometric assessments ≥ 1 week apart) is achieved.

- BOS progression is defined as ≥ 10% absolute decrease in FEV1 compared with
  pretreatment baseline observed in at least 2 consecutive spirometric assessments at least
  3 weeks apart. The onset of BOS progression is the earliest date of such qualified
  assessments.
- Time of loss of clinical benefit is the date when a participant discontinues treatment due to "lack of efficacy."

Participants with no observed BOS progression, loss of clinical benefit, or death at the time of database lock or discontinuation will be censored at the time of last valid FEV1 assessment.

Duration of FEV1 response will be assessed using the Kaplan-Meier method for participants who achieve a response. Median duration and 95% CIs will be estimated.

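### Withdrawal before Week 12 overrides an already confirmed FEV1 response in the rate (SAP 7.3, Protocol 10.4.1) but not in the duration analysis (SAP 7.4.1)

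*SAP*

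**What the plan says.** **Response rate.** SAP 7.3 defines the Phase 2 primary endpoint as the share of participants with at least a 10% absolute FEV1 increase at any point through Week 12, confirmed on two consecutive spirometry sessions at least a week apart. It then sets the rule: "If a participant withdraws from the study before Week 12", or has no FEV1 data to that visit, "the participant will be considered as a nonresponder". Protocol 10.4.1 has the same trigger ("If a participant withdraws from the study before Week 12, or there is no FEV₁ data up to and including Week 12") and the same consequence. Neither text exempts a response confirmed before the withdrawal.

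**Duration.** SAP 7.4.1 has its own onset rule: "The time of onset of response is defined as the earliest assessment date when" the confirmed rise is reached. Duration "will be assessed using the Kaplan-Meier method for participants who achieve a response". There is no Week 12 limit, no withdrawal condition and no reference to the status assigned in SAP 7.3. Participants who discontinue without progression, loss of benefit or death are censored at their last valid FEV1.

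**Phase 1.** SAP 7.3 closes by saying that the response rate is also calculated in Phase 1, because duration of response is a Phase 1 secondary endpoint. The nonresponder rule stands in the Phase 2 paragraph and is not restated.

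**Other uses.** SAP 8.2 models FEV1 response as a binary variable and compares responders with nonresponders, without naming the classification. Appendix A of the amended SAP still plans Table 2.1 (response), Table 2.3.1 (duration) and Listings 2.6.2 and 2.6.4.

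**The concern.** A nonresponder rule for early dropouts normally covers people whose outcome is unknown. Here it also covers people whose outcome is known. A participant who meets the confirmed definition at Weeks 4 and 8 has responded through Week 12 by the endpoint's own terms, and later withdrawal does not undo that.

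Two things are at stake. The response rate is pulled down by a rule that contradicts the definition it serves. The rate and the duration analysis can also rest on different responders, although SAP 7.3 justifies the Phase 1 rate by its link to duration. With 8 participants per dose level, one person is enough for the two tables to disagree visibly. An unstated flag also leaves a choice to be made after the data are known.

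**Working it through.** **1. The plan's own figure.** SAP 3.3 gives about 55 participants for Phase 2, with a 20% rate and a lower 95% limit above 5%. No power is stated. Assuming 80%, n = ((1.96 + 0.842) × √(0.20 × 0.80) / 0.15)² = 55.8, so 56. By the exact method that SAP 7.3 names, 11/55 has a 95% CI of 10.4% to 33.0%. The figure is reproduced to within one participant. Nothing below depends on it.

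**2. Can a response be confirmed before Week 12?** Protocol Table 2 schedules spirometry at Weeks 1, 2, 4, 8 and 12, with windows of ±7 days at Weeks 4, 8 and 12. Counting days from the start of treatment:
- latest Week 4 visit: 28 + 7 = 35; earliest Week 8 visit: 56 − 7 = 49; gap at least 14 days, which meets the one-week requirement;
- latest Week 8 visit: 56 + 7 = 63; earliest Week 12 visit: 84 − 7 = 77.

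A rise at Week 4 that is confirmed at Week 8 is complete before the Week 12 window opens.

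**3. One participant under each section.** Take a participant with a rise at Week 4, confirmed at Week 8, who withdraws from the study at Week 10 with no progression, loss of benefit or death.

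| Place | Status |
|---|---|
| Endpoint definition, SAP 7.3 | Responder: confirmed rise within the window |
| Withdrawal rule, SAP 7.3 and Protocol 10.4.1 | Nonresponder |
| Duration, SAP 7.4.1 | Responder: onset at Week 4, censored at last valid FEV1 |
| Responder comparisons, SAP 8.2 | Not stated |

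**4. Size in Phase 1, if the rule applies there.** Each affected participant takes one from the numerator and leaves the denominator unchanged, because the full analysis set keeps everyone dosed. At 8 per dose level the shift is 1/8 = 12.5 points. Exact 95% CIs:
- 2/8 = 25.0% (3.2 to 65.1) becomes 1/8 = 12.5% (0.3 to 52.7);
- 1/8 = 12.5% becomes 0/8 = 0% (0 to 36.9).

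If the participant is replaced under Protocol 5.5, the denominator is 9 and the shift is 1/9 = 11.1 points.

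**5. Direction for duration.** As written, SAP 7.4.1 keeps this participant, so nothing is removed from the Kaplan-Meier set. Suppose all the same that the participant were dropped. A censored time contributes only to the risk set at earlier event times. With an illustrative risk set of 5 and one event, the survival factor is 1 − 1/5 = 0.80. Without the censored participant it is 1 − 1/4 = 0.75. The curve stays level or falls; it does not rise.

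**The case against.** The best defence is that counting dropouts as nonresponders is a recognised conservative convention, set in advance and identical in protocol and SAP. No hypothesis is tested. The affected group is narrow, since the trigger is withdrawal from the study, and Protocol 7.1.1 and 7.1.2 let participants stop treatment and stay in follow-up. The rule stands in the Phase 2 paragraph, and Protocol 2.3 records that Phase 2 did not go ahead. With about 24 participants, the listings would show any mismatch.

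Much of this stands. It limits the size of the problem and makes the Phase 2 figures moot. It does not answer the contradiction. The convention is sound where the outcome is missing, but not where the endpoint has been observed and confirmed. The group is not empty by construction either: under Protocol 7.3 a participant who cannot be reached is treated as withdrawn, so loss to follow-up after a confirmed response triggers the rule. A listing would show a mismatch without settling which status is right.

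A reader might go further and infer that short responses are deleted from the duration analysis, so that duration is inflated and one of the two errors favours the drug. The documents do not support this. No text feeds the SAP 7.3 status into SAP 7.4.1, and plain withdrawal is censored, so even deletion could not raise the curve (step 5). Inflation would need both an unstated link between the sections and a response already ended by progression, loss of benefit or death before the participant withdrew.

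**Conclusion.** The concern holds as an internal contradiction. The withdrawal rule in SAP 7.3 and Protocol 10.4.1 overrides a confirmed response that meets the endpoint's own definition, and SAP 7.4.1 treats the same person as a responder. The response rate is biased downward, and the number entering the duration analysis can exceed the numerator of the rate. No bias in favour of the drug is shown.

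The live effect is in Phase 1: 12.5 points per affected participant at a dose level of 8. This assumes that the rule carries over to Phase 1, which the SAP leaves open, and that the full analysis set has 8 participants at that level. The documents do not say how many participants, if any, withdrew after a confirmed response, so the total effect is unknown and may be zero. The point is worth correcting because Tables 2.1 and 2.3.1 are both still planned.

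**What to change.** 1. In SAP 7.3 and Protocol 10.4.1, replace the rule with: *A participant who withdraws before Week 12 without a confirmed response, or who has no FEV1 measurement up to Week 12 inclusive, is a nonresponder.* Protocol 10.4.1 defines response without confirmation, so it needs the SAP's confirmation wording as well.
2. State that the rule applies to the Phase 1 response rate.
3. Derive confirmed response once and use it in SAP 7.3, 7.4.1 and 8.2. The rate counts confirmed responses through Week 12. Duration includes all confirmed responders, and those who first respond after Week 12 are identified. Restricting duration to a Week 12 flag would wrongly drop these late responders.
4. Keep the current rule as a sensitivity analysis beside Table 2.1.

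The cost is a few sentences and one extra row of output, with no new data. The primary rate becomes slightly less conservative. Because Protocol 2.3 reports that Phase 1 data were analysed in September 2021, the change should be declared in SAP 11.1, with both rates shown.
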